#### **9.11.7 OTHER EXPLORATORY PHARMACODYNAMIC ENDPOINTS**

JTXP was intended as an exploratory pharmacodynamics endpoint, but poor sample quality resulted in insufficient data for analysis.

### **9.12 INTERIM ANALYSES**

This is an open-label study. No formal interim analyses are planned. However, for Part C and Part D, the preliminary efficacy signal measured by the overall response rate (ORR),

will be evaluated using a group sequential design with 1 interim look for futility. The following hypotheses  $H_0: ORR \leq 0.08$  versus  $H_1: ORR \geq 0.20$  will be tested with a 90% power at a 2-sided  $\alpha=5\%$ . As the first step, 15 (Part C) or 15 (Part D) will be enrolled for each cohort in the current protocol. The anticipated total sample size for each cohort could be as large as 76 if warranted by the result obtained from the first 20 or 15 subjects. The following table lays out different scenarios based on the observed ORR from the first 20 or 15 subjects within each cohort:

Table 9 Operating Features of A Group Sequential Design with 1 Futility Interim Look at 20 or 15 Subjects with 90% Power and 2-sided  $\alpha=5\%$ .

Interim N	Interim $\beta$ spent	Futility Boundary	Interim result	Expand?	Total N	Final Result
20	0.1%	0	0 OR	Stop for futility	20	Non-significant
			$\geq 1$ ORs	Expand	76	If $> 10$ ORs, p-value $< 5\%$
15	0	0	0 OR	Stop for futility	15	Non-significant
			$\geq 1$ ORs	Expand	76	If $> 10$ ORs, p-value $< 5\%$

If the number of responses in any cohort of Parts C or D at interim look is more than the prespecified futility boundary based on the group sequential design, the study may enroll additional subjects for a more robust determination of efficacy.

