	
 Examine changes from baseline in gene signatures and immune cell subsets within tumor biopsies after treatment with JTX-2011 monotherapy (Part C) and JTX-2011 in combination with ipilimumab (Part F).
Study Drugs:	
 JTX-2011 is a humanized IgG1κ monoclonal antibody that is an agonist of Inducible CO-Stimulator of T cells (ICOS). Nivolumab, marketed as Opdivo[®], is a human IgG4κ anti-PD-1 monoclonal antibody manufactured by Bristol-Myers Squibb. Ipilimumab, marketed as Yervoy[®], is a human IgG1κ cytotoxic T-lymphocyte antigen 4 (CTLA-4)-blocking antibody manufactured by Bristol-Myers Squibb. Pembrolizumab, marketed as Keytruda[®], is a humanized IgG4κ anti-PD-1 monoclonal antibody manufactured by Merck.
Number of Subjects:	
Approximately 498 evaluable subjects will be enrolled, assuming the following:
 
 Part A: A total of 27 subjects were enrolled across six (6) dose levels. An additional 12 subjects were enrolled in the safety and PK/PD data (Safety/PK/PD Expansion Cohorts AP1 and AP2); Part B: A total of 16 subjects were enrolled across four (4) dose levels. An additional 15 subjects were enrolled in the safety and PK/PD data (Safety/PK/PD Expansion Cohorts BP1 and BP2); Part C: Approximately fifteen (15) subjects each in cohorts C01-C07 and C64 (approximately 120 subjects); Part D: Approximately fifteen (15) subjects each in cohorts D01-D06 (approximately 90 subjects). Part E: Approximately three (3) dose levels with a minimum of 3 or up to 6 subjects per dose level, exclusive of replacement subjects and evaluation of escalation dose levels (approximately 18 subjects); Part F: Approximately fifteen (15) subjects each in cohorts F61-F62 (approximately 30 subjects); Part G: Two (2) dose levels with a minimum of 3 or up to 6 subjects, exclusive of replacement subjects and evaluation of escalation dose levels (approximately 12 subjects); Part H: Approximately fifteen (15) subjects each in cohorts H31, H32, H33, and H35 (approximately 60 subjects) and approximately 49 subjects each in cohorts H34 and H64 (approximately 98 subjects).
Number of Centers:	Approximately 36 sites in North America

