## 4. STUDY DESIGN

This is a Phase 1/2, open label, multicenter, first-in-human trial to evaluate the safety and tolerability, PK, pharmacodynamics, and preliminary efficacy of the ICOS agonist monoclonal antibody JTX-2011 alone and in combination with nivolumab, ipilimumab, or pembrolizumab in adult subjects with advanced and/or refractory solid tumor malignancies. Phase 1 portion of the study contains 4 parts (Part A, Part B, Part E, Part G) with all parts completed following protocol design. Phase 2 portion also contains 4 parts (Part C, Part D, Part F, and Part H) but Part F and H never opened up for enrollment.

The study plans to enroll approximately 498 evaluable subjects at approximately 36 sites in North America.

Parts A and B comprise dose escalations in subjects with advanced solid tumors to assess the safety and tolerability, identify the maximum tolerated dose (MTD) and recommended Phase 2 dose (RP2D), and assess the PK and pharmacodynamics of JTX-

2011 alone and in combination with a fixed dose of nivolumab. Dose escalation scheme in Parts A and B follows the classical 3 + 3 design (more details in protocol section 6.2). Parts A and B also include expansion cohorts to collect additional safety, PK, and pharmacodynamics data in patients with  $\geq 1+$  ICOS expression levels (as determined by IHC) on archival tumor tissue or a history of documented PD1/PD-L1 expression.

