## 5. SAMPLE SIZE CONSIDERATIONS

For Part A, Part B, Part E, and Part G, the choice of the number of subjects is based on the classical 3 + 3 design. The approximate sample size in the dose escalation cohorts in Part A will be 36 evaluable subjects assuming that 6 subjects are assigned at each of 6 planned dose levels. The approximate sample size of the dose escalation cohorts in Part B will be 24 evaluable subjects assuming that 6 subjects are assigned at each of 4 planned dose levels. The approximate sample size of the dose escalation cohorts in Part E will be 18 evaluable subjects assuming that 6 subjects are assigned at each of 3 planned dose levels. The approximate sample size of the dose escalation cohorts in Part G will be 12 evaluable subjects assuming that 6 subjects are assigned at each of 2 planned dose levels.

Approximately 8 additional subjects will be enrolled in safety/PK/Pharmacodynamics expansion cohorts at each of 2 or more dose levels in Parts A (AP1, AP2) and B (BP1, BP2) to obtain additional safety and PK/Pharmacodynamics data. Subjects may also be added if exploration of intermediate dose level(s) of JTX2011 is warranted or if the SMC recommends adding additional subjects at a given dose level to further understand and clarify safety issues.

Approximately 120 subjects may be enrolled in Part C (approximately 15 in each cohort). Approximately 90 subjects may be enrolled in Part D (approximately 15 subjects per cohort). For Parts C and D, a group sequential design will be used to evaluate the preliminary efficacy of JTX-2011 or JTX-2011 in combination with nivolumab, with an interim look for futility. A 90% power at a 2-sided  $\alpha$  will be achieved for the hypothesis testing by enrolling 15 subjects (no more than 2% of  $\beta$  spent at interim) as the first step, and a potential expansion up to approximately 49 subjects per cohort if the futility boundary is passed based on the result from the first 15 subjects for each cohort. Using the same alpha and a non-binding futility analysis at 40% of evaluable subjects (17) with a Gamma spending function of -3 provides 80% power to rule out 13% in favor of 28%.

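### SAP Table 9 prints an interim beta of 0 for a stop rule that a cohort at 20% ORR meets 3.5% of the time, and SAP 5 ties 90% power to 49 subjects where SAP 9.12 needs 76

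*SAP*

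**What the plan says.** **SAP 9.12 (Parts C and D).** The test is ORR of at most 8% against at least 20%, with 90% power at two-sided 5%. On size: "The anticipated total sample size for each cohort could be as large as 76". The title of Table 9 begins: "Operating Features of A Group Sequential Design with 1 Futility Interim Look at 20 or 15 Subjects with 90% Power and 2-sided". The table has one row for a look at 20 subjects and one for a look at 15. Both stop on 0 responses and expand on 1 or more, and both declare p < 5% at more than 10 responses of 76. The interim beta column reads 0.1% (20) and 0 (15). The current first step is 15 subjects per cohort. Protocol 9.3 gives the same hypotheses and the same 76.

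**SAP 5 (also Parts C and D).** Of the 90% power it says: "will be achieved for the hypothesis testing by enrolling 15 subjects (no more than 2% of". The quantity limited there is the beta used up at the look. The same sentence describes the second step: "and a potential expansion up to approximately 49 subjects per cohort if the futility boundary is passed". It names no response rates and no value of alpha. The next sentence gives another set of inputs. On the timing of the look: "Using the same alpha and a non-binding futility analysis at 40% of evaluable subjects (17"). On what that design is said to deliver: "with a Gamma spending function of -3 provides 80% power to rule out 13% in favor of 28"%. The protocol synopsis (Sample Size Determination and Statistical Analyses) carries the same two sentences.

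**Where 49 is planned enrolment.** The synopsis (Number of Subjects) lists "approximately 49 subjects each in cohorts H34 and H64 (approximately 98 subjects") and about 15 for each Part C and Part D cohort. SAP 4 says of the remaining Phase 2 parts: "but Part F and H never opened up for enrollment".

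**The concern.** Table 9 presents itself as operating characteristics. A reader takes an interim beta of 0 to mean that the 15-subject look cannot discard a cohort at the target response rate. With a boundary of 0 responses in 15 that cannot be so. Table 9 is also the only prespecified basis for the stop-or-expand choice.

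The SAP also gives two maximum sizes for the same cohorts at the same 90% power. A reader of SAP 5 alone would credit a 49-subject Part C or D cohort with 90% power.

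**Working it through.** **Inputs.** From SAP 9.12: p0 = 0.08, p1 = 0.20, two-sided alpha 5%, power 90%, N = 76, looks at 15 or 20, stop on 0 responses, success at 11 or more. From SAP 5: N about 49; 13% vs 28%; 80% power; look at 17.

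**1. The plan's own 76.** Normal approximation for one proportion:

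n = [(z₀.₉₇₅·√(p0·q0) + z₀.₉₀·√(p1·q1)) / (p1 − p0)]² = [(1.960·√0.0736 + 1.282·√0.16) / 0.12]² = 75.7, so 76.

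Power at 76 by the same formula is 90.1%. The cut-off also reproduces under the normal score test: 11/76 gives z = 2.08, p = 0.0375; 10/76 gives p = 0.097.

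**2. Stop probability of the printed rule at ORR 20%.**

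| Look | Printed interim beta | P(0 responses) | Nominal O'Brien-Fleming-type spending of beta 0.10 |
|---|---|---|---|
| 15 of 76 | 0 | 0.8^15 = 3.52% | 0.02% |
| 20 of 76 | 0.1% | 0.8^20 = 1.15% | 0.13% |

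The last column matches the printed values after rounding. That origin is inferred, since no spending function is named for Table 9.

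**3. Effect on overall power (exact binomial, success at 11 or more of 76).** Without a look, power at 20% is 91.6%. The 15-subject look removes P(0 of 15) × P(at least 11 of the next 61) = 0.0352 × 0.699 = 0.0246, which leaves 89.1%. With the 20-subject look it is 90.9%. Exact one-sided type I error at 8% is 3.9% without a look and 3.7% with the 15-subject look.

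**4. Is 90% available at 49?** Power = Φ{[√n·(p1 − p0) − 1.960·√(p0·q0)] / √(p1·q1)}.

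- 8% vs 20%, n = 49: Φ[(0.840 − 0.532)/0.4] = Φ(0.771) = 78.0%.
- Exact, no look: at least 8 responses gives 79.1% (one-sided tail 3.9%); at least 9 gives 66.8% (tail 1.5%).
- 13% vs 28%: the formula in step 1 at 80% power gives n = 47.8, and power at 49 is 80.8%. At 90% power that design would need 68.

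So 49 does not give 90% power for either pair of rates, and it fits 13% vs 28% at 80%.

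**5. Where 49 belongs.** The synopsis total is 27 + 12 + 16 + 15 + 120 + 90 + 18 + 30 + 12 + 60 + 98 = 498. It is reached with 49 in each of H34 and H64 (the 98) and 15 in each Part C and D cohort (the 120 and 90).

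**6. The two interim fractions in SAP 5.** Read literally, 2% of a 10% beta is 0.2%. The nominal values in step 2 (0.02% and 0.13%) meet it; the actual stop probabilities (3.52% and 1.15%) do not. For the second design, 17/0.40 = 42.5 subjects, whereas 40% of 49 is 19.6 and 17/49 is 34.7%.

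**The case against.** The strongest reply is that little depends on these figures. SAP 3.3.1 disclaims formal hypothesis testing, SAP 7.10 and 7.11 rule out comparisons and significance, SAP 9.12 says that no formal interim analysis is planned, and expansion is permissive. ORR is reported descriptively. That limits the consequence. It does not reconcile 49 with 76, and SAP 9.12 itself says that the hypotheses will be tested at 90% power.

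A second reply is that the beta column is simply nominal and that 0 is 0.02% rounded. That is probably its origin. But nothing in the table says so, and once the boundary is rounded to 0 responses the nominal figure no longer describes the rule.

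A third is that the 90% sentence in SAP 5 names no response rates, so pairing it with 8% vs 20%, and pairing 49 with 13% vs 28%, are inferences. This stands. They rest on SAP 9.12 being the only other 90% design for these cohorts, on the recomputation, and on the enrolment table.

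Four stronger readings are tempting, and the documents do not support them:

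- *The 3.5% breaches a 2% cap.* The text caps 2% of beta, literally 0.2%, and the nominal entries meet that.
- *The 17 is an error.* The 40% refers to evaluable subjects, so about 42.5 evaluable among 49 enrolled is possible. Against this, the synopsis describes its total of 498 as evaluable. It is an ambiguity, not a proven mistake.
- *The 76 or the cut-off is wrong.* Both reproduce under the normal approximation.
- *The look spoils the 90%.* Exact power is still 89.1%.

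**Conclusion.** The point holds in two parts.

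First, Table 9's interim beta values are not those of its own rule. A cohort with a true ORR of 20% meets the 0-of-15 stop about 1 time in 28, where the table prints 0. The cost is 2.5 points of exact power (91.6% to 89.1%). That 89.1% belongs to the cut-off of more than 10 of 76, with its one-sided tail of 3.7%. At 12 or more responses it would be 83.7% with a tail of 1.6%.

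Second, for Parts C and D the SAP attaches the same 90% power to both 49 and 76. The 76 is right for 8% vs 20%. At 49 that comparison has about 78% (66.8% to 79.1% exact). The 49 fits 13% vs 28% at 80%, and the protocol plans enrolment of 49 only in H34 and H64 of Part H, which never opened.

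The stop probabilities assume independent responses at exactly 20%, and the power figures with a look assume that the stop is enforced. Only SAP Table 9 was checked, because the body of the protocol's Table 10 is not in the available text.

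**What to change.** **SAP 9.12, Table 9.** Label the beta column as nominal and add a column with the exact stop probability at ORR 20%: 3.5% at 15 and 1.15% at 20. State overall exact power of about 89% with the 15-subject look, together with its one-sided type I error of 3.7%. Make the same change in protocol Table 10 if it carries the same column.

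**SAP 5 and the matching protocol text.**

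- Tie 76 and 90% to 8% vs 20%.
- Tie 49 and 80% to 13% vs 28%, or delete that sentence for Parts C and D.
- Replace the limit on beta spent at the interim with the actual stop probability.
- If the 13% vs 28% sentence stays, state the evaluable N of which 17 is 40%.

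The cost is wording, with the signatures that a SAP update requires. It needs no extra subjects and no new analysis, and it leaves the stop at 0 responses and the cut-off of more than 10 of 76 unchanged.

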In **Part C**, **Part D**, **Part F** and **Part H** the preliminary efficacy signal, measured by the overall response rate (ORR), will be evaluated using a group sequential design with 1 interim look for futility. The following hypotheses $H_0: ORR \leq 0.08$ versus $H_1: ORR \geq 0.20$ will be tested with a 90% power at a 2-sided $\alpha=5\%$. As the first step, 15 (Part C) or 15 (Part D) or 15 (Part F) or 15 (Part H) subjects will be enrolled for each cohort in the current protocol. The anticipated total sample size for each cohort could be as large as 76 if warranted by the result obtained from the first 20 or 15 subjects. The following table lays out different scenarios based on the observed ORR from the first 20 or 15 subjects within each cohort:

Table 10: Operating Features of A Group Sequential Design with 1 Futility Interim Look at 20 or 15 Subjects with 90% Power and 2-sided $\alpha=5\%$.

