## 3.3 STATISTICAL HYPOTHESIS FOR EFFICACY

### 3.3.1 PRIMARY HYPOTHESIS

There is no formal hypothesis testing in either phase of this clinical trial protocol. The primary study endpoints of safety (for both Phase 1 and Phase 2) and the primary endpoints of efficacy (Phase 2) will be descriptively summarized for all study treatments and combinations.

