### **9.11.1 ANALYSIS OF RECIST v1.1 RESPONSE**

The best overall response (BOR) will be summarized by frequency and percent. The objective response rate (ORR) and disease control rate (DCR) estimates along with the corresponding exact 2-sided 95% CI using the Clopper-Pearson exact method will be provided. This will be done for the both the investigator and the central review response data. Subjects not classifiable under the RECIST 1.1 response categories due to insufficient data or early death will be classified as non-evaluable for BOR, but will be counted in the denominator of response rates (ORR, DCR) calculations.

Waterfall plots for best overall response and maximum percent change from baseline in tumor measurements and spider plots displaying the percent change from baseline in tumor measurements by study day will be displayed for evaluable and subset populations. Additional graphs by disease indication will be created as warranted. All RECIST response assessments will be listed by subject, cohort, phase and visit (including unscheduled). BOR, ORR and DCR will also be included.

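### SAP Table 9's success rule of more than 10 responses in 76 gives p below 5% only under an unnamed z test, and at 11/76 the SAP's own exact confidence interval still includes the 8% null

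*SAP*

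**What the plan says.** SAP 9.12 says that the ORR signal in Parts C and D "will be evaluated using a group sequential design with 1 interim look for futility". The null is ORR at most 0.08 and the alternative is ORR at least 0.20; these "will be tested with a 90% power at a 2-sided" alpha of 5%. On enrolment it says "As the first step, 15 (Part C) or 15 (Part D) will be enrolled for each cohort". Table 9 stops a cohort with no responses at 15 (or 20) subjects and otherwise expands it to 76. The final-result cell of both expansion rows reads "If $> 10$ ORs, p-value $< 5" per cent. No test is named for that p-value.

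Protocol 9.3 gives the same hypotheses, power and alpha, and says "The anticipated total sample size for each cohort could be as large as 76". The body of its Table 10 is not shown in the copy reviewed.

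For the same endpoint, SAP 9.11.1 says that the ORR estimate "along with the corresponding exact 2-sided 95% CI using the Clopper-Pearson exact method will be provided".

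SAP 3.3.1 states: "There is no formal hypothesis testing in either phase of this clinical trial protocol". SAP 7.10 rules out comparisons, and 7.11 marks statistical significance as not applicable. SAP section 5 describes expansion to roughly 49 subjects per cohort.

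**The concern.** Table 9 prints a significance threshold for a single-arm response rate, and 9.11.1 fixes an exact interval for that same rate. The two should give the same answer about the 8% null. With only 76 × 0.08 = 6.1 responses expected under the null, a normal approximation can differ from the exact binomial by enough to move the boundary by one response.

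At stake is how a cohort landing on the boundary would be reported. Under Table 9 it would carry a p-value below 5%; beside it would stand an interval that does not exclude the null rate. The chance of wrongly declaring activity would also be higher than the stated alpha implies.

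**Working it through.** **Inputs** (SAP 9.12 and Table 9): p0 = 0.08, p1 = 0.20, two-sided alpha 5% (upper tail 2.5%), power 90%, N = 76, success if X ≥ 11, stop for futility at 0/15 or 0/20. The interval method is from SAP 9.11.1.

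**1. Reproducing Table 9.** Use the one-sample z test with null variance and no continuity correction.
- N = [(1.960·√(0.08·0.92) + 1.282·√(0.20·0.80)) / 0.12]² = 75.7, so 76.
- Power at 76 = Φ[(0.12·√76 − 1.960·√(0.08·0.92)) / √(0.20·0.80)] = 90.1%.
- Critical count = 76·0.08 + 1.960·√(76·0.08·0.92) = 6.08 + 4.64 = 10.7, so more than 10.
- At 11/76, z = (11 − 6.08)/2.365 = 2.08, two-sided p = 0.0375.

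All four printed figures (76, more than 10, 90%, p below 5%) follow from this test.

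**2. The same result by exact binomial.**
- Upper tail: P(X ≥ 11 | 76, 0.08) = 0.0391.
- Two-sided p by doubling: 2 × 0.0391 = 0.078.
- Two-sided p by minimum likelihood: P(X ≥ 11) + P(X ≤ 1) = 0.0391 + 0.0135 = 0.053.
- Clopper-Pearson 95% limits for x/n are the 2.5% point of Beta(x, n − x + 1) and the 97.5% point of Beta(x + 1, n − x). For 11/76 they are 7.5% and 24.4%, so 8% is inside. For 12/76 they are 8.4% and 26.0%, so 8% is outside.

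**3. Other tests at 11/76** (two-sided p): doubled mid-p 0.056, continuity-corrected z 0.062, arcsine 0.071, Wald 0.109. Of the methods tried, only the uncorrected z test falls below 5%. Its matching Wilson interval has a lower limit of 8.3%.

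**4. Operating characteristics of the two boundaries.** With a stop at 0/m, the probability of success is the sum over x = 1 to m of P(X₁ = x | m, p) · P(X₂ ≥ r − x | 76 − m, p), where r is the boundary.

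| Boundary | Quantity | No look | Stop at 0/15 | Stop at 0/20 |
|---|---|---|---|---|
| ≥ 11 (Table 9) | Upper-tail error at 8% | 3.91% | 3.66% | 3.82% |
| ≥ 11 (Table 9) | Power at 20% | 91.6% | 89.1% | 90.9% |
| ≥ 12 | Upper-tail error at 8% | 1.73% | 1.64% | 1.70% |
| ≥ 12 | Power at 20% | 85.7% | 83.7% | 85.2% |

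Twelve is the smallest boundary at N = 76 whose exact upper tail is at or below 2.5%.

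**The case against.** The strongest reply is that Table 9 contains no arithmetic error. Step 1 shows that its figures come from a standard test, applied consistently. A reader might infer that the table was miscalculated, or that its alpha and power cannot both hold at 76. The documents do not support either inference: no test is named, and under the z test both hold. Exact power of the printed rule is also close to the stated 90%, at 89.1% with the 15-subject look and 90.9% with the 20-subject look.

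The size of the excess error depends on the benchmark. Counting both tails, the exact size of the z test at N = 76 is 3.91% + 1.35% = 5.25%, barely above 5%. If the 5% were read as one-sided, against the directional null, 3.9% would lie inside it. But the SAP states two-sided 5%, and the tail that declares activity is the upper one, so 2.5% is the relevant benchmark.

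The Clopper-Pearson interval in 9.11.1 is also a reporting method; nothing there says that it decides significance. That is correct, and the two methods agree at 10 or fewer and at 12 or more responses. They still disagree at the boundary itself, on the same endpoint in the same document.

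Finally, 3.3.1, 7.10 and 7.11 disclaim formal testing, expansion is optional, and section 5 has cohorts growing to about 49. These points stand and reduce the practical weight. They do not remove the printed rule, since 9.12 still says that the hypotheses are to be tested.

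**Conclusion.** The point holds as a matter of moderate weight. Table 9's claim is true under one unnamed approximate test. It is not true under an exact binomial test, and at exactly 11 of 76 it conflicts with the interval that 9.11.1 prescribes. The upper-tail error of the rule is 3.9% (3.7% with the 0/15 stop, 3.8% with the 0/20 stop) against an implied 2.5%. An exact boundary at the same N costs about 5 to 6 points of power.

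This rests on three assumptions: that two-sided 5% means 2.5% in the direction of activity, that a cohort is actually expanded to 76, and that the futility stop is followed when it is met. If cohorts stop near 49, or results are only described as 3.3.1 says, the boundary is never applied and the point concerns clarity only.

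**What to change.** Name the test behind Table 9, then choose one of two routes.

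- **Agree with 9.11.1.** In both expansion rows, change the boundary from more than 10 to more than 11 responses (at least 12/76). Restate power as about 84% with the 15-subject look or 85% with the 20-subject look.
- **Keep the boundary.** State that the p-value comes from the uncorrected z test. Give the exact one-sided error of 3.7% to 3.9% and exact power of 89% (15-subject look) or 91% (20-subject look). Add a note that 11/76 does not exclude 8% by the 9.11.1 interval.

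Make the same change in protocol Table 10 if it carries this boundary.

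The first route costs two table cells and one power figure, with a less favourable stated power. The second costs a sentence or two. Neither needs extra subjects or new data.
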